### **7.3.2. Consent**

Before committing to participate in the study, interested participants will be sent study materials to review. Participant information sheets will inform participants of the purpose of the research, how their data will be processed, used and stored, potential risks and benefits of taking part in the research and how to withdraw from the study if they choose to. They will also be sent a consent form to read.

Written consent will be obtained by all participants in advance of the interview or focus group, using econsent via electronic consent form, or remotely immediately before-hand, followed up by return of signed consent

Non-CTIMP & Studies Protocol -Version number: 1.0 IRAS ID: 335374

Page:

form in a stamped addressed envelope. Only participants that have the capacity to consent will be eligible to participate.

Participants will be given the opportunity to ask any questions on receipt of the study materials, and again at the start of the interview/ focus group, to make sure they are happy with everything and have no questions or concerns.

# 8. Safety reporting

There are no anticipated Adverse Events, Adverse Reactions and Serious Adverse Events resulting from this study due to it being non-interventional. In the unlikely scenario that an event occurs that is assessed by the CI as being serious, unexpected and possibly related to the study, these events will be reported in accordance with the sponsor's safety reporting procedures to the REC and Sponsor.

### 9. Ethical and regulatory considerations

Participants will be informed of potential risks and benefits associated with taking part in the study, detailed in the participant information sheet.

Participants will be informed that:

- Taking part in this study will help us to understand what pregnant women want and need from an
  intervention designed to inform about vaccinations during pregnancy. This will help us to tailor the
  information in an intervention to help them make an informed decision about whether to have a
  vaccination or not.
- There are no known disadvantages or risks associated with participating, other than the time it takes to take part. As the questions are related to the development of an intervention about vaccinations during pregnancy there is the possibility that discussions may discuss sensitive topics. Should this occur, the researcher will offer to pause or end the interview so as not to cause any upset. We expect that the interviews will take between 45-60 minutes depending on how much you have to say.

Whilst it is not anticipated that the interviews/ focus groups will cause participants any distress, researchers will be aware of any needs of the participants, and will offer to pause the interview/ focus group if they do become distressed. Support will be offered to participants if necessary in the form of relevant organisations, and signposting them to contact their GP.

Appropriate ethical approval will be sought on the methods and protocol prior to study commencement.

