### 9.1. Assessment and management of risk

Whilst we anticipate no risks we consider the following:-

- 1. Confidentiality and data protection risks for participants, to mitigate this study ID codes will be assigned to participant data with only authorised members of the study team having access to identifying links.
- 2. Potential risk of participants becoming upset during interviews, if this happens and the participant needs to take a break the interview will be paused and resumed if they are happy to continue or rescheduled.
- 3. Any potential risks identifying participants being at risk of harm to themselves or others during the study, if this happens local safeguarding procedures will be followed and participants will be advised to contact their healthcare professional. This may involve notifying participant's healthcare team, confidentiality will be breached in order to do so.

4.

- 5. IData integrity risks will be managed in line with the Data Management Plan (DMP) associated with the study.
- 6. If pregnant participants feel faint during an interview, the interview will be stopped, participants will be encouraged to contact their healthcare team and given the option to continue or reschedule when they feel well enough to proceed. If a participant becomes unresponsive medical attention will be sought (e.g. by dialling 999) and the interview will be stopped.

7. If a participant suffers a pregnancy loss following consent but prior to interview, it will be suggested to participants that the interviews/ participation is ceased so as not to incur upset to the participant.

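### The participant wording in section 9 denies any known risk beyond time, section 9.1 plans a safeguarding breach of confidentiality, and the protocol nowhere ensures that participants are told of that limit

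*Protocol*

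**What the plan says.** Protocol section 9 (Ethical and regulatory considerations) opens with a general commitment: "Participants will be informed of potential risks and benefits associated with taking part in the study, detailed in the participant information sheet". It then lists what participants will be informed of. The second bullet reads "There are no known disadvantages or risks associated with participating, other than the time it takes to take part". It continues that "there is the possibility that discussions may discuss sensitive topics", and that the researcher will then offer to pause or end the interview.

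Section 9.1 (Assessment and management of risk) begins "Whilst we anticipate no risks we consider the following" and gives a numbered list:

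- Item 1 is a confidentiality and data protection risk, mitigated by study ID codes and restricted access to the identifying link.
- Item 2 is "Potential risk of participants becoming upset during interviews".
- Item 3 covers participants found to be at risk of harming themselves or others. Local safeguarding procedures apply and the healthcare team may be notified. The protocol states that "confidentiality will be breached in order to do so".
- The remaining items deal with data integrity, faintness during an interview and pregnancy loss before interview.

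Section 7.3.2 (Consent) says the information sheets will cover "how their data will be processed, used and stored, potential risks and benefits of taking part in the research". The sheets are listed by title in Appendix 3, and their text is not shown.

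**The concern.** Section 9 goes further than saying that risks will be explained. It supplies a sentence to be conveyed to participants, and that sentence rules out any known risk beyond time. Section 9.1 names risks that the sentence leaves out. The important one is item 3, because it is a step the protocol already plans to take if a certain kind of disclosure is made.

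A limit on confidentiality bears directly on what a person chooses to say. If the wording in section 9 were followed as it stands, a participant could speak on an inaccurate description of what may happen to the information. Objective 1 gives particular attention to less-visible groups, and the Phase 1 sampling section relies on community routes because they have built trust in earlier research. It is a reasonable inference, though not a documented one, that an unexpected breach would do most damage there, both to the participant and to recruitment.

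**Working it through.** No arithmetic decides this point, and the plan gives no figure to reproduce. The check is a comparison of the risks in section 9.1 with the participant wording in section 9, followed by a search of the other sections for the safeguarding limit.

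**Step 1. Risk by risk.**

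| Section 9.1 | Participant wording in section 9 | Result |
|---|---|---|
| Item 1: confidentiality and data protection | Not mentioned | Conflicts with the statement that only time is a known burden |
| Item 2: upset | Sensitive topics acknowledged, with an offer to pause or end | Largely disclosed |
| Item 3: notification of the healthcare team, with confidentiality broken | Not mentioned | Planned step, undisclosed in this wording |
| Item 5: data integrity | Not mentioned | Not a risk to the participant |
| Item 6: faintness | Not mentioned | An event that may happen during an interview, not described as caused by taking part |
| Item 7: pregnancy loss before interview | Not mentioned | Not a risk of taking part |

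Item 4 is blank. Two items carry the finding: item 1 and, above all, item 3.

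**Step 2. Is the limit disclosed elsewhere in the protocol?**

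- Section 7.3.2 (Consent) promises information on risks and on data handling in general terms. It does not mention a safeguarding exception.
- Section 9 does not mention it.
- The section on data protection and patient confidentiality restricts study data to the researchers and states no exception.
- The section on access to the final dataset restricts audio files and transcripts to the research team and states no exception.

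Section 9.1 is therefore the only place where the limit appears, and it describes what the team will do, not what participants will be told.

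**Step 3. Who is reached.** The targets are up to 40 women and 20 clinicians in Phase 1 and about 20 women in Phase 2. Phase 1 women may continue into Phase 2, so the number of different women lies between 40 + 0 = 40 and 40 + 20 = 60. Section 9 speaks of participants generally, but clinicians have their own information sheet, so it is not shown that they receive the same sentence. The protocol gives no expected number of safeguarding disclosures, and none can be derived.

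**The case against.** The strongest reply is that the protocol is not the document participants read. Section 9 says risks are detailed in the information sheet, section 7.3.2 says the sheet covers data handling, and Appendix 3 lists three sheets and two consent forms. Any of these could state the safeguarding limit, and the ethics committee must give a favourable opinion on the protocol and consent forms before the study starts. Section 9.1 is also framed as contingencies under a statement that no risks are expected, which is closer to section 9 than a bare list would be. Finally, the same bullet does acknowledge sensitive topics.

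Most of this stands, and it narrows the point. Upset is substantially disclosed. Faintness, data integrity and pregnancy loss should not be counted as contradictions. What the sheets say is unknown.

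It does not remove the point. If the sheets follow section 9, they carry the same inaccuracy. If they differ, the protocol and the sheets disagree. In both cases section 9 needs correcting. Calling item 3 a contingency does not reconcile the sections either: however unlikely, it is a planned response that overrides confidentiality.

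A reader might also infer that the stated 45–60 minutes understates the burden, because Phase 2 women are invited to two interviews. The documents do not support that. The figure reads as the length of one interview and matches the Phase 1 sampling section, the two Phase 2 interviews are stated in the study summary and in section 7.2, and Phase 2 consent is taken at the start of each interview.

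**Conclusion.** The point holds in a limited form. Sections 9 and 9.1 are inconsistent on confidentiality, and the protocol does not ensure that participants learn of the safeguarding limit before they speak. This is more than missing detail, because section 9 fixes wording that is inaccurate on a matter relevant to what a participant discloses.

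A reader might go further and conclude that participants will disclose without knowing the limit, or that consent is undermined. That would require the information sheets and consent forms to be silent, and they are not shown. The conclusion here rests only on the protocol text.

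The effect cannot be put as a number. It concerns the protection of participants and the accuracy of the consent information, and has no bearing on the analysis. The change is worth making before recruitment begins.

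**What to change.** 1. In section 9, replace the sentence that denies any risk beyond time. The new wording should name the confidentiality and data protection risk and the possibility of upset. It should also say plainly that confidentiality may be broken, and the healthcare team notified, if there is concern about harm to the participant or to others.
2. Adjust the opening of section 9.1 so that it agrees with the revised section 9.
3. Check the information sheets for women and for clinicians against this wording and align them where they differ.
4. State in section 7.3.2 that the limit is repeated verbally at the start of each interview or focus group. Participants are already invited to ask questions at that moment, so no new step is needed.

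The cost is wording in the protocol and, where needed, the sheets, with whatever amendment review the sponsor or ethics committee advises. The one downside is that taking part is described slightly less favourably.

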### 9.1. Assessment and management of risk

Whilst we anticipate no risks we consider the following:-

- 1. Confidentiality and data protection risks for participants, to mitigate this study ID codes will be assigned to participant data with only authorised members of the study team having access to identifying links.
- 2. Potential risk of participants becoming upset during interviews, if this happens and the participant needs to take a break the interview will be paused and resumed if they are happy to continue or rescheduled.
- 3. Any potential risks identifying participants being at risk of harm to themselves or others during the study, if this happens local safeguarding procedures will be followed and participants will be advised to contact their healthcare professional. This may involve notifying participant's healthcare team, confidentiality will be breached in order to do so.

4.

- 5. IData integrity risks will be managed in line with the Data Management Plan (DMP) associated with the study.
- 6. If pregnant participants feel faint during an interview, the interview will be stopped, participants will be encouraged to contact their healthcare team and given the option to continue or reschedule when they feel well enough to proceed. If a participant becomes unresponsive medical attention will be sought (e.g. by dialling 999) and the interview will be stopped.

7. If a participant suffers a pregnancy loss following consent but prior to interview, it will be suggested to participants that the interviews/ participation is ceased so as not to incur upset to the participant.

#### 9.2. Research Ethics Committee (REC) and other Regulatory review & reports

Before the start of the study, a favourable opinion will be sought from a REC for the study protocol, informed consent forms and other relevant documents e.g. advertisements. The research team will follow the following principles:

- Substantial amendments that require review by NHS REC will not be implemented until that review is in place and other mechanisms are in place to implement at site.
- All correspondence with the REC will be retained.
- It is the Chief Investigator's responsibility to produce the annual reports as required.
- The Chief Investigator will notify the REC of the end of the study.
- An annual progress update will be submitted to the sponsor within 30 days of the anniversary date of the approval of the study and annually until the study is declared ended.
- If the study is ended prematurely, the Chief Investigator will notify the REC, including the reasons for the premature termination.
- Within one year after the end of the study, the Chief Investigator will submit a final report with the results, including any publications/abstracts, to the REC.

### **Regulatory Review & Compliance**

The following regulatory review and compliance issues have been considered:

- Before any site can enrol patients into the study, the Chief Investigator or designee will ensure
  that appropriate approvals from participating organisations are in place. Specific arrangements
  on how to gain approval from participating organisations are in place and comply with the
  relevant guidance.
- For any amendment to the study, the Chief Investigator or designee, in agreement with the sponsor will submit information to the appropriate body in order for them to issue approval for the amendment. The Chief Investigator or designee will work with sites (R&D departments at NHS sites as well as the study delivery team) so they can put the necessary arrangements in place to implement the amendment to confirm their support for the study as amended.

## **Amendments**

Any amendments to the study will involve amendments to the protocol, which will be logged with a new version number and date. A log of amendments will be maintained with version number, date and reason for change.

The research team will seek advice from sponsorship and/or REC regarding whether an amendment is substantial or non-substantial.

All changes will be communicated to relevant stakeholders by email, detailing the changes made, reasons for changes, and accompanied by an updated protocol.

### 9.3. Peer review

The study has been peer reviewed by the funder (NIHR RfPB) during the two stage funding application process. 9.4 Patient & Public Involvement

This study have received Patient & Public Involvement (PPI) input throughout the design and development phases of the study, including prior to the grant application being submitted.

The study will have a PPI group consisting of four members of the public, a lay member of the advisory group, and a PPI co-applicant who will attend research group meetings. PPI involvement will be fundamental to all stages of the process.

### 9.4. Protocol compliance

Accidental protocol deviations can happen at any time. They must be adequately documented on the relevant forms and reported to the Chief Investigator and Sponsor immediately.

Deviations from the protocol which are found to frequently recur are not acceptable, will require immediate action and could potentially be classified as a serious breach. While it is not anticipated that serious breaches are applicable in this study, any incidents identified that are likely to affect to a significant degree the safety or mental integrity of the participants or scientific value of the study will be reported as serious breaches to the REC and study Sponsor in accordance with the Sponsor's serious breaches reporting procedures.

The study quality will be assured by frequent study management meetings, advisory meetings and PPIE meetings. Updates on progress and any challenges will be discussed at these meetings. Additionally, required reports will be submitted to the funder where appropriate.

### 9.5. Data protection and patient confidentiality

All investigators and study site staff must comply with the requirements of the Data Protection Act 2018 with regards to the collection, storage, processing and disclosure of personal information and will uphold the Act's core principles.

Any hard copies of documents (personal data from pregnant women or midwives expressing an interest in participation) will be destroyed after data is entered digitally. Until the information is entered digitally it will be stored in a locked cabinet at University of Birmingham, in a locked office, completely separate to the research data. Only named study researchers will have access to the key for the cabinet.

Any hard copy consent forms will be scanned and stored in a password protected file on an encrypted university network drive at University of Birmingham. Once scanned and stored hard copies of consent forms will be destroyed in confidential waste. Electronic consent forms will be held completely separately from the research data. Only named study researchers will have access to the password protected files. They will be retained for 10 years and then destroyed, in line with University policy. Audio files of the verbal consent will be stored on a University of Birmingham server in a separate location to the interview transcript data, accessible only to the researchers and password protected, saved on encrypted University network drives. At the end of the study the files will be archived according to University archiving policy and deleted after 10 years.

Interview transcripts will be pseudonymised or allocated a unique ID and stored digitally. All study data will be stored only on University servers, where access to this data is restricted to only the study researchers. Key to pseudonyms or IDs will be saved in a password protected document, separate from interview files.

When publishing the study, we will provide contextual information about the participating pregnant women and clinicians, but this will be presented in aggregate and will not allow individuals to be identified. In publishing the interview study we will use quotes from the interviews. We will ensure that these are fully pseudonymised and any contextual information provided will not identify the patient.

The University of Birmingham research team will have access to the study data. All team members will adhere to the collaboration agreement between University Hospitals Coventry and Warwickshire and the University of Birmingham within which sits the data sharing agreement.

#### 9.6. Indemnity

This study will be covered by indemnity insurance of the sponsor; the University of Birmingham.

The University of Birmingham has in place Clinical Trials indemnity coverage for this trial which provides cover to the University for harm which comes about through the University's, or its staff's, negligence in relation to the design or management of the trial and may alternatively, and at the University's discretion provide cover for non-negligent harm to participants.

With respect to the conduct of the trial at Site and other clinical care of the patient, responsibility remains with the NHS organisation responsible for the clinical site and is therefore indemnified through NHS Resolution. The NHS have a duty of care to participants whether or not the participant is taking part in a clinical trial and the normal NHS complaints mechanisms will apply.

#### 9.7. End of study and archiving

This is a 15 month study, which will be considered complete once data collection, data analysis and dissemination has been finished.

At the end of the study the files will be archived according to University archiving policy and deleted after 10 years.

#### 9.8. Access to the final study dataset

The research team will have access to the final dataset. The data analysis will be conducted by the Chief Investigator and the Research Fellow (RF), but additional members of the research team may be asked to contribute to analysis, and would therefore have access to anonymised transcripts. Only the Chief Investigator and RF will have access to the audio files.

Consent forms reflect possible use of data for secondary analysis.

### 10. Dissemination policy

#### 10.1. Dissemination policy

The main output from this study is the production of a complete intervention, that aims to inform pregnant women and their families about vaccinations. Following analysis, a final report will be prepared. This report will be submitted to the funder, and publication of results will be developed by the research team.

Dissemination of findings to the public:

Summaries of the findings from the qualitative research (what pregnant women and clinicians told us they want from an intervention), and on the development process of the intervention will be shared with members of the public and stakeholders via women's organisations and social media groups. Participants will also be given the opportunity during the consent process to indicate they would like to receive a summary of the findings.

A summary of findings, infographics and blogs will also be shared on a dedicated study webpage hosted by the University of Birmingham.

Dissemination to healthcare professionals:

Summaries of findings, infographics and blogs will be shared with clinicians. This will include presentations to clinician team meetings (such as midwife team meetings).

Findings will contribute to e-learning modules (for organisations such as Royal College of General Practitioners and Royal College of Midwives), designed to provide education of strategies to employ to encourage vaccination uptake amongst pregnant women.

Dissemination to wider academic audience:

We will publicise findings at local and national conferences (such as the annual MBBRACE conferences or Royal College of Midwives annual conference), in open-access journals, on relevant social media (such as via MAMTA's social media pages), University of Birmingham webpages and press releases.

Dissemination to policymakers and professional bodies:

Summary of findings sheets for vaccination and maternal health policymakers and professional bodies (including NHS England, MBRRACE and JCVI) will be available to download via dedicated study webpages on University of Birmingham website, and will be shared to professional bodies using established contacts within the research team.

Representatives from policy and professional organisations will be invited to attend a dissemination event to discuss the findings and future recommendations at the end of the study.

Any IP arising from the study will be owned by the University of Birmingham. The funders will be acknowledged in all reporting of the results (publications, conference presentations etc).

